#### 4.1.1 **Dosing regimen**

Following a screening period of up to 4 weeks participants will receive 4 (Part 1) or 2 (Part 2) single oral doses of RO7017773.

The following treatments will be administered in Part 1 (4 period crossover):

- Treatment A: Phase I capsule swallowed whole under fasted conditions
- Treatment B: Phase II tablet swallowed whole under fasted conditions
- Treatment C: Phase II tablet swallowed whole under fed conditions
- Treatment D: Phase II tablet dispersed in water under fasted conditions (taste assessment)

The following treatments will be administered in Part 2 (2 period crossover) in different participants to Part 1:

- Treatment A: Phase II tablet containing flavor and/or sweetener dispersed in water under fasted conditions (taste assessment)
- Treatment B: Phase II tablet without flavor and/or sweetener dispersed in apple juice under fasted conditions (taste assessment)

#### **4.1.2 Length of the Study**

##### **Part 1- 4 Period Crossover**

The total duration of the study for each participant will be approximately 9 weeks divided as follows:

- Screening: Up to 4 weeks.
- In clinic periods: Day -1 to Day 3 for each of the 4 treatments.
- Treatment Periods: Day 1 to Day 5 for each of the 4 treatments (with single dosing on Day 1 of each period).
- Washout period 7 to 10 days (washout period is counted from Day 1 dose, i.e., overlapping with treatment period).
- Safety follow-up: 7 to 14 days after last dose.

##### **Part 2 – 2 Period Crossover**

The total duration of the study for each participant will be approximately 7 weeks divided as follows:

- Screening: Up to 4 weeks.
- In clinic Periods: Day -1 to Day 3 for each of the 2 treatments.
- Treatment Periods: Day 1 to Day 5 for each of the 2 treatments (with single dosing on Day 1 of each period).
- Washout period 7 to 10 days (washout period is counted from Day 1 dose, i.e., overlapping with treatment period).
- Safety follow-up: 7 to 14 days after last dose.

#### **4.1.3 Individual Stopping Criteria**

Dosing will be stopped at any time during the study in a given individual participant if one of the following circumstances occurs, unless it is determined by the Investigator that the occurrence is not related to the administration of the study drug:

- a serious adverse event
- one (or more) severe adverse events
- clinically significant changes in vital signs or ECG, such as a QTcF > 480 ms (if confirmed by repeated measurement within 30 minutes) or QTcF change-from-baseline > 60 ms (if confirmed by repeated measurement within 30 minutes)
- an elevation of ALT > 3 x ULN, with an associated increase in bilirubin > 2 x ULN and with ALP > 2 ULN, in the absence of an alternative explanation
- other findings, that at the joint discretion of the sponsor clinical pharmacologist, the sponsor safety science leader and the investigator, indicate that dosing in this individual should be stopped

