## **7.1 DISCONTINUATION OF STUDY TREATMENT**

See the SoA ([Section 1.3](#)) for data to be collected at the time of treatment discontinuation and follow-up and for any further evaluations that need to be completed.

Discontinuation of study intervention for abnormal liver function should be considered by the Investigator when a participant meets one of the conditions outlined ([Section 6](#), [Appendix 3](#)) or if the Investigator believes that it is in best interest of the participant.

Participants who discontinue study treatment prematurely will be asked to return to the clinic for a study completion visit and may undergo follow-up assessments (see [Section 8.10.3](#)). The primary reason for premature study treatment discontinuation should be documented on the appropriate eCRF. Participants who discontinue study treatment prematurely may be replaced Participants who discontinue study treatment due to safety reasons will not be replaced.

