### **8.3.6 Non-Serious Adverse Events of Special Interest**

Non-serious adverse events of special interest are required to be reported by the Investigator to the Sponsor immediately (i.e., no more than 24 hours after learning of the event; see [Appendix 2](#) for reporting instructions).

Non-serious adverse events of special interest for this study include the following:

- Cases of an elevated ALT or AST in combination with either an elevated bilirubin or clinical jaundice, as defined in [Appendix 3](#).
- Suspected transmission of an infectious agent by the study treatment, as defined below:

Any organism, virus, or infectious particle (e.g., prion protein transmitting transmissible spongiform encephalopathy), pathogenic or non-pathogenic, is considered an infectious agent. A transmission of an infectious agent may be suspected from clinical symptoms or laboratory findings that indicate an infection in a patient exposed to a medicinal product. This term applies only when a contamination of the study treatment is suspected.

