## 2. **DEFINITION OF SERIOUS ADVERSE EVENTS**

If an event is not an AE per definition above, then it cannot be a serious adverse event (SAE) even if serious conditions are met (e.g., hospitalization for signs/symptoms of the disease under study, death due to progression of disease).

A serious adverse event is defined as any untoward medical occurrence that at any dose:

- **Results in death.**
- **Is life-threatening.**

The term "life-threatening" in the definition of "serious" refers to an event in which the participant was at risk of death at the time of the event; it does not refer to an event which hypothetically might have caused death if it was more severe.

- **Requires inpatient hospitalization or prolongation of existing hospitalization** (see [Appendix 3](#)).

In general, hospitalization signifies that the participant has been detained (usually involving at least an overnight stay) at the hospital or emergency ward for observation and/or treatment that would not have been appropriate in the physician's office or outpatient setting. Complications that occur during hospitalization are AEs. If a complication prolongs hospitalization or fulfills any other serious criteria, the event is serious. When in doubt as to whether "hospitalization" occurred or was necessary, the AE should be considered serious.

Hospitalization for elective treatment of a pre-existing condition that did not worsen from baseline is not considered an AE.

- **Results in persistent or significant disability/incapacity**

Disability means substantial disruption of the participant's ability to conduct normal life functions.

This definition is not intended to include experiences of relatively minor medical significance such as uncomplicated headache, nausea, vomiting, diarrhea, influenza, and accidental trauma (e.g., sprained ankle) which may interfere with or prevent everyday life functions but do not constitute a substantial disruption.

- **Is a congenital anomaly/birth defect.**
- **Other significant events:**

Medical or scientific judgment should be exercised in deciding whether SAE reporting is appropriate in other situations such as important medical events that may not be immediately life-threatening or result in death or hospitalization but may jeopardize the participant or may require medical or surgical intervention to prevent one of the other outcomes listed in the above definition. These events should usually be considered serious.

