#### **3.1. ASSESSMENT OF SEVERITY**

The Investigator will make an assessment of severity for each AE and SAE reported during the study and assign it to one of the categories provided in [Table 1](#) (as a guidance for assessing adverse event severity).

The terms "severe" and "serious" are not synonymous. Severity refers to the intensity of an adverse event (rated as mild, moderate, or severe, or according to a pre-defined grading criteria [e.g., National Cancer Institute Common Terminology Criteria for Adverse Events [NCI CTCAE] criteria]; the event itself may be of relatively minor medical significance (such as severe headache without any further findings).

Severity and seriousness need to be independently assessed for each adverse event recorded on the eCRF.

Serious adverse events are required to be reported by the Investigator to the Sponsor immediately (i.e., no more than 24 hours after learning of the event).

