## **6. ABNORMAL LIVER FUNCTION TESTS**

The finding of an elevated ALT or AST ( $>3 \times \text{ULN}$ ) in combination with either an elevated total bilirubin ( $>2 \times \text{ULN}$ ) or clinical jaundice in the absence of cholestasis or other causes of hyperbilirubinemia is considered to be an indicator of severe liver injury. Therefore, investigators must report as an adverse event the occurrence of either of the following:

- Treatment-emergent ALT or AST  $>3 \times \text{ULN}$  in combination with total bilirubin  $>2 \times \text{ULN}$ .
- Treatment-emergent ALT or AST  $>3 \times \text{ULN}$  in combination with clinical jaundice.

The most appropriate diagnosis or (if a diagnosis cannot be established) the abnormal laboratory values should be recorded on the Adverse Event eCRF (see [Appendix 2](#)) and reported to the Sponsor immediately (i.e., no more than 24 hours after learning of the event), either as a serious adverse event or a non-serious adverse event of special interest (see [Section 8.3.6](#)).

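### The liver item in Section 4.1.3 requires raised ALP and omits AST and jaundice, so the non-cholestatic pattern that Appendix 3 ties to severe liver injury cannot trigger it, and a narrow set of events is left to judgement

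*Protocol*

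**What the plan says.** **The stopping item.** Protocol Section 4.1.3 lists the circumstances that end dosing for an individual, unless the Investigator determines that the occurrence is unrelated to study drug. The liver item is ALT above 3 x ULN that comes "with an associated increase in bilirubin > 2 x ULN and with ALP > 2 ULN, in the absence of an alternative explanation". The other items are a serious adverse event, one or more severe adverse events, significant vital-sign or ECG changes, and other findings at the joint discretion of two sponsor roles and the Investigator.

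**The severe-injury pattern.** Appendix 3 Section 6 names ALT or AST above 3 x ULN combined with total bilirubin above 2 x ULN or "clinical jaundice in the absence of cholestasis or other causes of hyperbilirubinemia is considered to be an indicator of severe liver injury". Its two reporting triggers contain no ALP condition. Such a case goes to the Sponsor within 24 hours "either as a serious adverse event or a non-serious adverse event of special interest". Section 8.3.6 lists "Cases of an elevated ALT or AST in combination with either an elevated bilirubin or clinical jaundice" among the non-serious events of special interest.

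**The discontinuation section.** Section 7.1 states: "Discontinuation of study intervention for abnormal liver function should be considered by the Investigator when a participant meets one of the conditions outlined", and points to Appendix 3 Section 6.

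**Eligibility at Day -1.** Section 5.2 applies the exclusion criteria at screening and Day -1. Exclusion 13 bars ALT and/or bilirubin above 1.5 x ULN, except isolated bilirubin that has been fractionated with direct bilirubin below 35%. Exclusion 12 bars clinically significant laboratory abnormalities, including the hepatic panel.

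**The concern.** Section 4.1.3 is where site staff look for an individual stop. Its liver item demands a raised ALP, while Appendix 3 attaches its warning to cases without cholestasis. The item therefore leaves out the pattern that the protocol itself treats as the most worrying. It also leaves out cases driven by AST and cases recognised by jaundice.

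The participants are healthy volunteers. After an event in Part 1 period 1, 2 or 3, there are 3, 2 or 1 doses still due; in Part 2, one dose is due after the first period. If no other rule applies, the default for such an event is that the Investigator considers stopping, not that dosing stops unless the event is judged unrelated.

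**Working it through.** The plan gives no figure to reproduce, so the check is one of logic.

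**Step 1. The two rules as conditions.** Take five yes/no conditions: ALT > 3, AST > 3, bilirubin > 2, jaundice, ALP > 2 (laboratory values x ULN). They give 2^5 = 32 patterns.

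- Section 4.1.3 item: ALT and bilirubin and ALP. AST and jaundice are free, so 2 x 2 = 4 patterns.
- Appendix 3 laboratory/jaundice condition: (ALT or AST) and (bilirubin or jaundice), ALP free. That is 3 x 3 x 2 = 18 patterns, which include all 4 above.
- Of the 18, those with ALP not above 2 number 3 x 3 = 9. The item covers 0 of them.
- Of the other 9, with ALP above 2, the item covers 4 and misses 5: 3 with AST but not ALT raised, and 2 with ALT raised and jaundice but bilirubin not above 2.

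These are logical patterns, not probabilities.

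**Step 2. An illustration.** ALT 10, AST 8, bilirubin 4 (x ULN) with ALP at or below ULN meets the first Appendix 3 trigger. It cannot meet the 4.1.3 item, and no higher ALT or bilirubin would change that.

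**Step 3. What else could prevent the next dose.**

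| Route | Effect on such a case |
|---|---|
| Serious adverse event (4.1.3) | Stop unless judged unrelated. Not automatic: Appendix 2 Section 2 says of important medical events "These events should usually be considered serious", but Appendix 3 also permits non-serious classification. |
| Severe adverse event (4.1.3) | Stop unless judged unrelated. Open either way: the severity table grades disruption of daily activity and is offered "as a guidance for assessing adverse event severity". |
| Exclusion 13 at Day -1 | Numeric bar on ALT and bilirubin, whatever the ALP, with no relatedness exception. No AST term. |
| Exclusions 1, 12 and 14, inclusion 4 | May apply, by judgement. |
| Section 7.1; other findings in 4.1.3; sponsor discussion in Section 8 | Judgement. |

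**Step 4. How far exclusion 13 reaches.** Table 5 puts the eligibility review and blood chemistry at Day -1 under the heading for study days in each period. Footnote f limits only randomization to Period 1. Section 5.3.1 refers to safety laboratory tests on Day -1 and Day 3, and Sections 5 and 8 bar waivers. The natural reading is a check before every dose.

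Doses are 7 to 10 days apart, so the next dose falls on Day 8 to 11 of the current period's count and the next Day -1 on Day 7 to 10. That is 4 to 7 days after the Day 3 tests. To pass, the case in Step 2 would need ALT to fall by a factor of 10/1.5 = 6.7 and bilirubin by 4/1.5 = 2.7 (unless the bilirubin exception applied). A case just over the thresholds would need factors of about 3/1.5 = 2 and 2/1.5 = 1.3. The documents give no rate of recovery, so how often this could happen is unknown.

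**Step 5. What is left.** The event must be classed non-serious and not rated severe. In addition, either ALT and bilirubin fall to 1.5 x ULN or lower before the next Day -1, or exclusion 13 does not bite. It does not bite if AST alone stays high, or if the Day -1 review is read as first admission only. In these cases every remaining route in Step 3 is one of judgement.

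**The case against.** The strongest reply is that the protocol already handles this pattern. Exclusion 13 is a numeric bar and, while values stay raised, is stricter than Section 4.1.3, because the Investigator cannot set it aside as unrelated. Section 7.1 ties liver discontinuation to the Appendix 3 conditions, so AST, jaundice and normal-ALP cases are not overlooked. Repeat testing under Section 8.2.4, the Day 4 and Day 5 visits and 24-hour reporting should make the event known before the next dose. Every item in 4.1.3 yields to the Investigator's relatedness judgement in any case.

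Most of this stands, and it narrows the point. It does not close it. Exclusion 13 looks at values on one day, so it says nothing about a rise that has settled, and it has no AST term. Section 7.1 asks for consideration only. Testing, visits and reporting bring the event to light but set no stop.

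A reader might infer that a volunteer with severe liver injury would be dosed again, or that the protocol has no stop for such a case. The documents do not support that: the serious and severe items and exclusion 13 would catch many such events. Nor can it be said that the item fires on small rises and ignores large ones; any such contrast depends on the ALT and ALP values chosen for the example.

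**Conclusion.** The mismatch is real and lies in the current text of Section 4.1.3, Section 7.1 and Appendix 3 Section 6. No redaction touches the liver criteria. Its practical reach is limited to the events in Step 5. For those, aligning the item would change the default from considering a stop to stopping unless judged unrelated. For events classed serious or rated severe, that default already applies and nothing changes.

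Two assumptions matter. First, Appendix 3 gives no ALP cut-off for cholestasis; I take ALP of 2 x ULN or lower as the non-cholestatic case. Second, I read the Day -1 review as applying in every period; if it means first admission only, the gap is wider. No risk is quantified, because the visible documents give no liver event rate. This is a modest safety-consistency correction worth making.

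**What to change.** Replace the liver item in Section 4.1.3 with: *treatment-emergent ALT or AST above 3 x ULN together with total bilirubin above 2 x ULN or clinical jaundice, with no alternative explanation*. Keep the existing lead-in on relatedness. Add a cross-reference to 4.1.3 in Section 7.1. The new item covers all 18 patterns, including the 4 covered now, and a cholestatic or other cause can still be weighed as an alternative explanation.

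**Cost.** A protocol amendment, with IRB/EC and authority approval as locally required (Appendix 1 Section 2.3.1). No new tests are needed, since ALT, AST, ALP and bilirubin are in the chemistry panel.

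There may be a rare extra stop, and Section 7.1 says: "Participants who discontinue study treatment due to safety reasons will not be replaced". The effect on Part 1 depends on timing. In the four sequences ABCD, BDAC, CADB and DCBA, both A and B (the primary comparison) have been received in 0, 1 and 2 sequences after periods 1, 2 and 3, so in 0 + 1 + 2 = 3 of 12 sequence-by-period combinations. Part 1 enrols 16 to obtain at least 12 evaluable participants. The PK population asks only for one dose and one post-dose sample, subject to its exclusions.

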### **4.2 SCIENTIFIC RATIONALE FOR STUDY DESIGN**

The study rationale is provided in [Section 2.1](#).

A crossover design is used in each study part to reduce the residual variability as every subject acts as their own control. Subjects will be randomized to treatment sequences in each study part to minimize assignment bias. A washout of at least 7 days between RO7017773 doses is considered sufficient to prevent carryover effects of the treatments.

#### **4.2.1 Rationale for Study Population**

The participants of this study are healthy males and women of non-childbearing potential (WONCBP) aged 18 to 55 years (inclusive), chosen because of the absence of confounding diseases, which will enable a clearer and more consistent assessment of drug disposition and safety profile.

#### **4.2.2 Rationale for Pharmacokinetic Assessments**

The investigation of relative bioavailability of the Phase II tablet formulation compared to the Phase I capsule formulation is the primary objective of the study. Pharmacokinetic assessments of RO7017773 will be performed in plasma. The timings of PK samples collection are based on PK modelling and on observed PK data collected in study BP40091 and are considered adequate to allow for the characterization of the absorption, distribution and elimination phases RO7017773 following a single oral dose of the Phase I capsule and Phase II tablet formulation. Sample collection up to Day 5 is considered to be sufficient to allow for a reasonable estimation of the half-life of RO7017773.

Plasma PK samples may also be screened for exploratory RO7017773 metabolite identification with the use of non-validated methods to allow for an early identification of

the metabolite(s) formed in vivo, and in particular to determine if any human-specific metabolite(s) are produced. In such circumstances, metabolite concentrations may be measured in residual pharmacokinetic plasma samples retrospectively, as appropriate.

#### **4.4 END OF STUDY DEFINITION**

A participant is considered to have completed the study if he/she has completed all treatment periods within Part 1 or Part 2 and the safety follow-up visit.

The end of the study is defined as the date when the last participant last observation (LPLO) occurs. LPLO is expected to occur approximately 2 weeks after the last participant's last dose.

#### **5. STUDY POPULATION**

The study population rationale is provided in [Section 4.2.1](#).

The participants of this study are healthy participants between 18 and 55 years of age, inclusive, who fulfill all the inclusion criteria listed in [Section 5.1](#) and none of the exclusion criteria listed in [Section 5.2](#).

Prospective approval of protocol deviations from recruitment and enrollment criteria, also known as protocol waivers or exemptions, is not permitted.

#### **5.1 INCLUSION CRITERIA**

Participants are eligible to be included in the study only if all of the following are met at screening and Day -1:

##### **Informed Consent**

1. Able and willing to provide written informed consent and to comply with the study protocol according to International Conference on Harmonisation Good Clinical Practice (ICH-GCP) guidelines and local regulations.

##### **Age**

2. Participants 18 to 55 years of age inclusive, at the time of signing the informed consent.

##### **Type of Participants and Disease Characteristics**

3. Non-smoker for at least six months.
4. Healthy, as judged by the Investigator.

Healthy status will be defined as the absence of evidence of any active or chronic disease following a detailed medical and surgical history, a complete physical examination, vital signs, 12-lead ECG, hematology, blood chemistry, serology and urinalysis.

##### **Weight**

5. Body mass index (BMI) within the range 18 to 32 kg/m^2 (inclusive).

## Sex

### 6. Male and female participants

The contraception and abstinence requirements are intended to prevent exposure of an embryo to the study treatment. The reliability of sexual abstinence for male and/or female enrollment eligibility needs to be evaluated in relation to the duration of the clinical study and the preferred and usual lifestyle of the participant. Periodic abstinence (e.g., calendar, ovulation, symptothermal, or post-ovulation methods) and withdrawal are not acceptable methods of contraception.

#### a) Female Participants

*Only women of non-childbearing potential (WONCBP) are allowed to be enrolled in this study.*

A female participant is eligible to participate if she is not pregnant (see [Appendix 5](#)), not lactating, and the following condition applies:

- Women of non-childbearing potential, as defined in [Appendix 5](#), who have a negative pregnancy test (blood) within the 28 days prior to the first study drug administration.

*Additional contraceptive measures are only required if menopausal status or non-childbearing potential is not completely certain. In this instance, one of the non-hormonal highly effective contraception methods described in [Appendix 5](#) should be used during the treatment period and for at least 28 days after the last dose of study drug.*

#### b) Male Participants

During the treatment period and for at least 28 days after the last dose of study drug agreement to:

- Remain abstinent (refrain from heterosexual intercourse) or use contraceptive measures such as a condom, with partners who are women of childbearing potential (WOCBP, as defined in [Section 1 of Appendix 5](#)), or pregnant female partners, to avoid exposing the embryo.
- Refrain from donating sperm for at least 28 days after the last dose of study drug.

